1.3. Preclinical Experience

Not Applicable

1.4. Clinical Studies

We and others have published using cashew or shrimp food allergen OIT (Andorf, et al. 2018, Begin et al. 2014, Muraro, et al. 2017, Wood, et al. 2017, Paviqua, et al. 2010). Most of the studies are phase 1 and phase 2 studies to test safety and to optimize dosing.

Under IND [REDACTED] we have dosed more than 50 participants (4-55 yrs) with cashew or shrimp allergies. The key goal of the IND was to develop a customized regimen for oral immunotherapy that reflected what the participant was allergic to in a clinically significant way (i.e., the offending food allergen is defined as a food allergen with a positive skin test or positive specific IgE and a positive DBPCFC). We also followed participants long term (out to 8 yrs +).

Few studies have been conducted to identify the immunological mechanism(s) underlying any long-lasting effects of OIT, currently termed “sustained unresponsiveness”, or to address the safety of ingesting a food allergen for a prolonged period of time. To address these questions in the field of food allergy research, we designed a phase 1 study to test the long-term safety of multi-food OIT. We enrolled children and adults (4-55 years of age) with proven severe multiple food allergies that include peanut, and/or milk, and/or egg, and/or tree nut, and/or seed and/or wheat. Entry criteria for the study included allergen-specific IgE ≥ 7 kU/L or skin test reactivity to each food item ≥ 5 mm wheal diameter and a clinical history consistent with an allergic reaction to each of these foods within 1 hour of ingestion, as well as positive double-blinded, placebo-controlled food challenges (DBPCFC performed separately) for each food allergen (Andorf, et al. AACI 2017. <https://www.ncbi.nlm.nih.gov/pmc/articles/PMC5738818/>).

The active phase of the study was approximately 12 months, and the follow up phase was approximately 12 months. Clinical and laboratory-based assessments were performed for safety parameters in addition to blood sampling for translational/mechanistic studies. Careful monitoring occurred every two weeks and daily diaries were collected. Safety data were collected as per Good Clinical Practice guidelines and allergic reactions were defined as those adverse events related to study drug vs non-allergic adverse events were defined as those events not related to study drug. Of 50 participants enrolled, 12 withdrew (3 moved out of state, 6 switched to food equivalents, and 3 were non-compliant with reaction medications—i.e. each of the 3 had substituted herbal medicines for antihistamine medicines). In total, there were 24,606 doses of study drug over approximately 24 months for each participant and 1227 adverse events related to study drug (about 3.3%).

Overall, at the end of the study, participants were able to escalate to the top dose of each of their allergens (4g of protein). There were no SAEs. There were no cases of life threatening anaphylaxis. There were no cases of angioedema, respiratory, or cardiovascular compromise. The most frequent reaction involved skin/subcutaneous tissues and was mild (58%). Out of the 1227 adverse events related to study drug, 10 reactions were defined as severe or Grade 3 Bock's criteria per protocol (Andorf, et al. 2017. <https://www.ncbi.nlm.nih.gov/pmc/articles/PMC5738818/>). Although this is a phase 1 study and neither blinded, nor controlled, the data seem to suggest a satisfactory safety profile (compared to historical literature). No reaction had any sequelae after treatment.

There are several lines of evidence showing that the protection afforded by OIT wanes over time if withdrawal occurs, however, some participants have been able to discontinue therapy and yet remain able to tolerate doses of food allergen that would have provoked a reaction prior to therapy. Studying sustained unresponsiveness (SU) will help us define new targets (in food allergen specific T cell subsets and other cellular compartments) for longer lasting effects in OIT and will help us understand the mechanisms of OIT and possible sustained, long term successful clinical outcomes. Therefore, we have added a 6-week discontinuation period to our study. There does not seem to be any increased risk of severe allergic reactions due to the 6 weeks discontinuation (Andorf, et al. 2019 Burks et al. 2012); therefore, we have chosen this rather than a longer time period to monitor participants.

2. Study Hypotheses/Objectives

We hypothesize that OIT to cashew or shrimp results in distinctive patterns of T cell responses throughout the course of treatment and that these patterns can be revealed by immunophenotyping of cells responding to specific epitopes. If proven correct, the results will aid in the development of tools for T cell reagents for cashew, and shrimp allergens, and provide a platform for developing a diagnostic program for FA OIT response. We also hypothesize that the results will advance our knowledge of FA prognosis.

2.1. Primary Objective(s)

To determine T cell, immune-based mechanisms of food allergy and to optimize T cell reagent discovery and validation by obtaining blood samples from FA participants undergoing OIT, and simultaneously, develop diagnostic, prognostic, and mechanistic tools based on the T cell reagents developed during the course of OIT.

2.2. Secondary Objective(s)

- Identify, characterize, and validate new T cell epitopes for important food allergens (cashew, shrimp)
- Track the numbers and functions of epitope-specific T cells during stages of FA OIT
- Associate these parameters with phenotype and endotype characterizations in food-allergic individuals
- Determine whether immune monitoring measurements reflecting these underlying mechanisms can be used to predict responses to OIT

2.3. Exploratory Clinical objectives:

- To evaluate desensitization protocols for cashew and shrimp in allergic individuals
- Determine whether the achievement of sustained unresponsiveness is different between cashew or shrimp food allergy participants after a period of withdrawal from OIT
- Exploring changes in the transcriptomes and phenotypes of tetramer+ T cells from baseline to 52 weeks, 58 weeks, and to 64 weeks.

2.4. Safety Objectives

- The proportion of participants with only mild AEs during the course of the study.
- The proportion of participants with respiratory or abdominal severe AEs during the course of the study.
- The proportion of participants who successfully pass a DBPCFC with no or mild objective reactions to a cumulative 2043 mg of the FA allergen at the end of OIT (desensitization, week 52).
- The proportion of participants who successfully pass a DBPCFC with no or mild objective reactions to a cumulative 2043 mg of the FA allergen after 6 weeks off OIT (sustained unresponsiveness, week 58) as completed (please see Appendix 2).

[figure not shown]
3. Study Design

3.1. Description of Study Design

This is a prospective Phase 2, single-center, single-allergen OIT in cashew or shrimp in participants with proven allergies to either cashew or shrimp, respectively. Our intent is to treat a total of 72 participants, ages 7 to 55 years, with an allergy to either cashew or shrimp determined by Double Blind-Placebo Controlled-Food Challenges (DBPCFC), allergy history, clinical symptoms, food-allergen (FA)-specific IgE levels, and skin prick test (SPT). Enrolled participants must be positive at or before the 300 mg (443 mg cumulative) dosing level of FA protein. OIT treatment groups will be cashew or shrimp, total number of participants (n=72).

Screening phase (Week -52 to Week 0): Under an existing protocol IRB-approved ‘Prescreening Protocol’ at Stanford, and this protocol, we propose to screen approximately 100 individuals ages 7-55 years, of both sexes. Participants will initially be screened for the FA using blood test and SPT. If participants show positive IgE and SPT to more than one of the studied FAs (cashew, shrimp), they will undergo multiple DBPCFCs that will be performed on different days. Participants must be positive at or before the 300 mg (443 mg cumulative) dosing level of FA protein in accordance with PRACTALL (Practical Issues in Allergology) consensus guidelines, regardless of how they were initially diagnosed as food-allergic. No more than 52 weeks should elapse between the qualifying DBPCFC and the initial dosing day.

Figure 1. A Prospective Pilot Phase 2 Study in Cashew- or Shrimp-allergic Participants

Enrollment phase (Week 0/Day 1): After assuming a 50% screening success (based on our previous phase 2 studies and their screening- to- enrollment ratio), we plan to enroll 72 participants as the intent-to-treat population. Participants will be enrolled onto the OIT treatment groups. If a participant has 2 out of the 2 FA, then the allergen will be chosen based on research needs with respect to patient preference. .

Updosing phase (Week 1 to Week 28): All cohorts will undergo an updosing regimen starting at 5 mg allergen, with dose escalation every 2 weeks to reach a maximum maintenance dose of 1000 mg dose at Week 28. We expect active OIT treatment subjects to reach 1000 mg of allergen protein (cashew or shrimp) between 26 to 28 weeks. Participants who have not reached 1000 mg by week 28 will continue to be up dosed, if considered safe, until week 52. In case of unforeseen circumstances that make an in-person visit in clinic difficult, doses may need to be sent to the participant’s home.

Maintenance phase (Week 28 to Week 52): Once participants get to the 1000 mg dose at week 28, they will stay on that dosage until Week 52. At week 52, participants will undergo DBPCFC. Participants that pass their food challenge with no or mild objective reactions to up to a cumulative 2043 mg of the FA allergen in their OIT at the end of this phase (primary outcome) will be considered desensitized and have successfully met the primary endpoint.

Withdrawal phase (Week 52 to Week 58 and Optional Week 64): Withdrawal from OIT will occur for 6 weeks, from week 52 to week 58 for all participants (Refer to Appendix 2 for participant disposition). This withdrawal phase is designed to examine mechanisms underlying sustained unresponsiveness (SU). SU will be defined as a participant’s

passing a DBPCFC with no or mild objective reaction to up to a cumulative 2043 mg of the FA allergen in their OIT at week 58. We chose a 6-week period of withdrawal based on prior studies (Andorf et al, 2018, Burks, et al. New England Journal of Medicine, 2012). If the participant passes the Week 58 DBPCFC up to a cumulative of 2043 mg, he/she will be given the option to continue avoidance until Week 64 and perform another set of DBPCFCs to further assess SU.

End of study (Week 58 or Week 64): Participants will be followed until week 58 or until Week 64 for those who choose to continue avoidance beyond Week 58). Participants will be given guidance on how to consume real food equivalents based on their current tolerated dose. (Appendix 2).

Participant Disposition (see Appendix 2):

Any participant that at least can tolerate 300 mg of FA protein will continue to dose at 300 mg and will be asked to come back at week 52, and 58 for blood and/or skin tests.

Any participant that terminates early or who reaches week 58 or the optional Week 64 , will be referred to an allergy practitioner for further follow up and clinical care.

Mechanistic controls:

We will compare our results against non treated mechanistic controls with similar clinical characteristics. These mechanistic controls are historical controls that are allergen-matched and clinically matched as best as possible. These participants consent for blood sampling under a separate IRB-approved consent.

Figure 2. Study Flow Chart

Timepoint/Visit	Screen	Week 0 / Day 1	Every 2 wks (Weeks 0-28 or until maintenance reached)	Week 52	Week 58 /End of Study	Week 64 (Optional)	
Informed Consent		x					
Medical History	X						
Physical Assessment	X	X	X	X	X	X	
Con Meds	X	X	X	X	X	X	
Adverse Events	X	X	X	X	X	X	
Specific IgE/IgG4*	X			X	X	X	
Skin testing	X			X	X	X	
Blood for T cell studies*	X	X		X	X	X	
Urine pregnancy test	X						
Lung Function	X	X	X	X	X	X	
Diaries		X	X	X	X	X	
Inject Epi training	X			X	X		
Fecal samples	X			X	X		
DBPCFC	X			X TEST DESENSITIZATION	X TEST SU	X TEST SU	
OIT (cashew or shrimp)		X	X				
QOL questionnaires*	X	X		X	X		

*If unable to perform at both screening and Week 0, sample from either visit will suffice.

In case of unforeseen circumstances that make an in-person visit in clinic difficult, doses may need to be sent to the participant's home.

We plan to identify the basic immune mechanisms monitored by epitope-specific T cell methods which could potentially explain the differences in the effects of OIT in individuals who do or do not become clinically tolerant and to determine whether immune monitoring can predict the safety and efficacy outcomes in OIT protocols, and predictors of re-emergent allergic reactivity. After initial screening and enrollment, there are three phases of the study (Figure 1):

- Dose escalation and Build up Phase
- Maintenance phase
- Withdrawal phase

Treatment Failures:

- Treatment failures will be defined as those participants who withdraw or who are withdrawn due to unacceptable side effects of OIT by week 52
- If participants demonstrate moderate or severe clinical reactivity (Appendix 3) in DBPCFC at week 58, they will be considered desensitized but SU failures.

All participants who start home dosing of OIT will be considered in statistical analyses of the intent-to-treat population.

Integration with mechanistic science program: This is a pilot, prospective, phase 2 clinical trial to study safety and dosing of OIT; in addition, the clinical trial's mechanistic purpose is to provide blood samples to identify the basic immune mechanisms monitored by epitope-specific T cell methods which could explain the differences in the effects of OIT in individuals. Based on our results (Ryan, et al. PNAS 2016, Syed, et al. JACI 2014) (IND [REDACTED] and IND [REDACTED]) we expect significant differences in food- allergen epitope-specific T cell immunophenotypes and clinical outcomes with the total sample size proposed here.

Study Design Safety Considerations

The design considers important safety issues:

- All uposing visits will be supervised in a hospital setting where trained study physicians are available.
- Standing orders from an MD are provided for all clinical study personnel (RN, NP, PA, etc.) to initiate treatment of reactions immediately (i.e., prior to MD notification), including IM administration of epinephrine, based on their own clinical judgment.
- A crash cart with pediatric and adult equipment is available in close proximity of all patient hospital rooms.
- A code team is available for pediatric and adult patients.
- Dosing symptoms and adverse events will be captured throughout the study.
- Subjects will be prescribed an epinephrine auto-injector (if not prescribed by a treating clinician previous to study entry) and all subjects will be trained in its use.

Subjects will be cautioned against consuming any foods containing the FA allergen they are being treated for, other than study-supplied food allergen while on study.

3.2. Primary Endpoint(s)/Outcome(s)

Change in expression of CD28 in the CD4+ allergen specific (CD154+) T-cells at 52 weeks relative to baseline values between those who do and do not pass a cumulative of 2043 mg at the DBPCFC at week 52.

3.3. Secondary Endpoint(s)/Outcome(s)

- Compare changes in expression of CD28+ allergen specific (CD154+) T-cells over multiple time points from baseline to week 58 and week 64 between those with sustained unresponsiveness (SU) vs those desensitized but SU failures vs those who do not pass the desensitization DBPCFC:
- Compare changes in the following measures in CD4+CD28+ allergen specific (CD154+) T-cells at week 52 and week 58 between those who achieved sustained unresponsiveness (SU) vs those desensitized but SU failures vs those who did not pass desensitization DBPCFC at week 52
 - Levels of IFN-gamma
 - levels of IL-4
 - Receptor diversity in allergen specific T cell CDR3b as compared to non-specific T cells
 - levels of IL-10
 - levels of TGF-beta
 - levels of GPR15
 - Levels of CCR4+
 - Levels of CRTh2

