1.2. Rationale for Selection of Investigational Product or Intervention

We have designed the primary endpoint based on preliminary mechanistic understandings of T cell modifications over time during immunotherapy. When first activated, T-cells initially start making Th2 products like IL4 and IL13, but over the course of therapy they start making more interferon gamma and start expressing less CD28 so that they appear more anergic (Ryan et al. PNAS 2016; Syed, et al. JACI 2014; Pellerin, et al. JACI 2018). The hypothesis would be to expect a change of 20% in the T cell population to shift within 52 weeks toward this activated allergen-specific subset that makes interferon gamma and is more anergic. Exploratory endpoints will include the changes in the transcriptomes and phenotypes of tetramer+ T cells from baseline to 52 weeks, 58 weeks and to 64 weeks.

Our and others' community-based participatory research⁷⁻⁹ show that many patients and families would prefer to be desensitized to a low dose of FA protein (300mg) to avoid worry about accidentally eating a contaminated food, while others would prefer to safely ingest a larger dose of FA protein (1,000 mg or more) to be able to try certain foods containing the FA; therefore, we have proposed using these two quantities in our clinical study as the treatment dose (1000 mg) and the desensitization threshold (2,043 mg). There are several lines of evidence (Jones, et al. AAAAI, 2018, Phase 3 results of PALISADES study and Andorf, et al. AACI 2017

<https://www.ncbi.nlm.nih.gov/pmc/articles/PMC5738818/>) demonstrating that 300 mg of maintenance of each food allergen protein will allow some protection in the majority of participants to at least 1000 mg of each food allergen protein during a standardized food challenge. However, recent data has shown that maintenance at higher levels (i.e. 1000 mg) would afford protection to higher levels of accidental ingestion (for shrimp, since the average shrimp is approximately 8g, we prefer to propose 1000 mg maintenance in this study) and perhaps could improve SU outcomes.

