8.5. Visit Windows

Study visits should take place within the time limits specified below: the designated visit windows (i.e. +/- n days) for each scheduled visit are also indicated on the Table of Events.

Table 3: Visit Windows*

Visit Type	Target Date	Visit Window
------------	-------------	--------------

Screening/Baseline/Randomization	Day -364 to 1	Day -364 to Day 1
Initial dose day	Day 1	Within 364 days from screening
Dose Escalation Phase	Weeks 2, 4, 6, 8, etc. until maintenance dose is reached	±7 days
Maintenance Phase	Weeks 28 to 52	
Tolerance Phase	Weeks 52 to 58 and up to optional Week 64	

* in the time of an epidemic, doses might need to be sent to the participant’s home at the same dose.

9. Mechanistic Assays

Comparisons for each of the parameters discussed below could occur between:

- On Treatment vs. Baseline for each participant, and
- SU vs. Desensitized but SU Failures clinical outcomes at week 58 DBPCFC.
- Desensitized vs all others at week 52 DBPCFC

I) Serum Assays

Serum Assays

Panel	Volume needed for each sample collection
Specific IgE, IgG4, IgA anti-food allergen and the component-resolved testing where applicable	1 ml
Epitope Arrays	350 microliters

Expected Results for Serum Parameters

Parameter	Desensitization	SU
Specific IgE And Specific IgG4	Progressive decrease in specific IgE to food allergen (FA) and increase in specific IgG4	Low specific IgE and increased IgG4
Epitope Array for IgE for FA peptides— predictive marker for outcome	Progressive Inhibitory antibodies present in epitope array	Intermediate epitope spreading at baseline
Specific IgA	Progressive increases in specific IgA over time	Intermediate levels of specific IgA

Note: Compared to placebo, in which we assume no changes will occur.

II) Cell components for CyTOF

Expected Results for Cell Parameters

Parameter	Desensitization	SU
Th2	Progressive decrease in Th2 absolute numbers and ICS transcription factors and Th2 cytokines	Low Th2 cells and low ability to proliferate in response to FA
Anergy	Decreased CD28 and CD38	Lack of CD28 and CD38
Th1	Progressive increase in Th1 absolute numbers and ICS transcription factors and Th1 cytokines	High Th1 cell numbers and ability to proliferate in response to FA
Th17	Do not expect change	Do not expect change
Treg	Progressive increase in absolute counts of Treg but then decline by 12 mo.	Intermediate Treg cell numbers and decreased ability to proliferate in response to FA

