13.2.2 Secondary Endpoint(s)/Outcome(s)

- Compare changes in expression of CD28+ allergen specific (CD154+) T-cells over multiple time points from baseline to week 58 and week 64 between those with sustained unresponsiveness (SU) vs those desensitized but SU failures vs those who did not pass the desensitization DBPCFC.
- Compare changes in the following measures in CD4+CD28+ allergen specific (CD154+) T-cells at week 52 and over multiple time points through week 58 between those who achieved sustained unresponsiveness (SU) vs those desensitized but SU failures vs those who did not pass the week 52 (desensitization) DBPCFC
 - Levels of IFN-gamma
 - levels of IL-4
 - Receptor diversity in allergen specific T cell CDR3b as compared to non-specific T cells
 - levels of IL-10
 - levels of TGF-beta
 - levels of GPR15
 - levels of CCR4+
 - levels of CRTh2
- Changes in distribution of immune cells representing difference in regulatory T cells vs eosinophils and mast cells over multiple time points obtained with GI biopsy tissues across those who achieved sustained unresponsiveness (SU) vs those desensitized but SU failures vs those who did not pass the week 52 DBPCFC.

Expectations:

- Comparing sustained unresponsiveness (SU) vs desensitized but SU failures, there will be at least a 50% increase in the absolute allergen tetramer + T-cell numbers at week 58.
- Comparing SU vs desensitized but SU failures. There will be at least a 20% change in the allergen specific (CD154+) T-cell activation towards a Th1/ anergic state at week 58 DBPCFC.
- Comparing desensitized vs all other failures, there will be increased IFN γ , decreased IL-4, and increased T cell receptor diversity in allergen specific T cells as compared to non-specific T cells at week 52.

- Comparing SU vs desensitized but SU failures, there will be increased IFN γ , decreased IL-4, and increased T cell receptor diversity in allergen specific T cells as compared to non-specific T cells at week 58.
- Comparing SU vs desensitized but SU failures, allergen specific T cells from participants with mild to no allergic reactions on DBPCFC at week 58 will demonstrate increased IL-10, TGF- β , GPR15, and less T cell receptor diversity.

Other Endpoints:

- Comparing the proportion of participants who become desensitized vs all others (i.e. treatment failures) at week 52 DBPCFC.
- Comparing the proportion of participants who reach SU vs desensitized but SU failures at week 58 DBPCFC.

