13.6 Statistical Hypotheses

Our hypothesis is that CD28 expression in the allergen specific (CD154+ or tetramer+) T-cell activation towards a Th1/ anergic state at week 52 DBPCFC relative to baseline will be significantly decreased among those who achieve desensitization versus those who do not.

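### The cytokine, receptor and TCR secondary endpoints are defined only in CD28+ cells, although the plan expects successful OIT to lower CD28, so a predicted IFN-gamma rise may be attenuated or missed

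*Combined protocol and SAP*

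**What the plan says.** The synopsis and section 3.3 give the same stem for eight secondary measures: "Compare changes in the following measures in CD4+CD28+ allergen specific (CD154+) T-cells at week 52 and week 58". Section 13.2.2 keeps the gate and changes only the timing: "Compare changes in the following measures in CD4+CD28+ allergen specific (CD154+) T-cells at week 52 and over multiple time points through week 58". The measures are IFN-gamma, IL-4, CDR3b receptor diversity, IL-10, TGF-beta, GPR15, CCR4 and CRTh2.

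The primary endpoint in section 3.2 has no CD28 gate: "Change in expression of CD28 in the CD4+ allergen specific (CD154+) T-cells at 52 weeks relative to baseline values".

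On mechanism, section 1.2 says of the T cells that "over the course of therapy they start making more interferon gamma and start expressing less CD28 so that they appear more anergic". It expects 20% of the T cell population to "shift within 52 weeks toward this activated allergen-specific subset that makes interferon gamma and is more anergic". Section 13.6 states the hypothesis that CD28 expression "relative to baseline will be significantly decreased among those who achieve desensitization versus those who do not". In the section 9 table of expected cell results, the anergy row reads "Decreased CD28 and CD38" for desensitization and "Lack of CD28 and CD38" for SU.

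The Expectations in 13.2.2 predict changes in IFN-gamma, IL-4, IL-10, TGF-beta, GPR15 and receptor diversity. Where they name a population it is allergen specific T cells, with no CD28 restriction. Section 13.4.4, which describes the analysis of these markers, names no cell population. No CD28 positivity threshold is given anywhere.

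**The concern.** CD28 is the primary outcome variable, and the plan expects treatment to lower it more in responders. If the secondary measures are taken only in cells that are still CD28+ at week 52 or 58, the cells entering each participant's measurement are chosen by a post-treatment value of that outcome. The CD28+ compartment would then differ in size and make-up between the response groups being compared.

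The risk is clearest for IFN-gamma, because section 1.2 says the cells that come to make it are the cells whose CD28 falls. A null result inside the gate could mean that nothing changed, or that the change happened in cells outside the gate. The trial's primary objective concerns T cell mechanism and these measures are a main mechanistic readout, so that ambiguity matters even at secondary level. The stated endpoints and the stated Expectations also refer to different cell populations.

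**Working it through.** The plan gives no figure for this point, so there is nothing to reproduce. The check sets the definitions side by side and then asks what a CD28+ gate would show under the plan's own expected shift.

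**Populations named**

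| Place | Population |
|---|---|
| Primary endpoint, 3.2 | CD4+CD154+ |
| Eight secondary measures: synopsis, 3.3, 13.2.2 | CD4+CD28+CD154+ |
| Expectations, 13.2.2 | allergen specific T cells |
| Analysis text, 13.4.4 | not named |
| Bulk sort, 13.7 | activation-positive T cells, no CD28 restriction stated |

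**Inputs.** The 20% shift is from section 1.2, read here as 20 of every 100 allergen-specific cells. Everything else is assumed, because the documents give no marker shares: 5% of cells are CD28-negative at baseline, and the IFN-gamma+ shares are as listed below.

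**Case 1: shares within each subset stay fixed.** Let p₊ and p₋ be the IFN-gamma+ shares in CD28+ and CD28-negative cells. If 20% of cells move from CD28+ to CD28-negative, then

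ungated change = (0.25·p₋ + 0.75·p₊) − (0.05·p₋ + 0.95·p₊) = 0.20·(p₋ − p₊).

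| p₊ | p₋ | Ungated change | Change in CD28+ gate |
|---|---|---|---|
| 5% | 20% | 3 points | 0 |
| 10% | 40% | 6 points | 0 |
| 10% | 60% | 10 points | 0 |
| 20% | 80% | 12 points | 0 |

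The zero in the last column follows from holding p₊ fixed. It is the case in which the whole rise sits in CD28-negative cells.

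**Case 2: new producers arise among CD28+ cells and some of them lose CD28.** Take 100 cells, 95 of them CD28+, with 10% IFN-gamma+ in both subsets (9.5 in the gate). Twenty CD28+ cells newly make IFN-gamma, and a fraction h of those become CD28-negative.

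- Ungated: 10/100 to 30/100, a rise of 20 points.
- Gated: from 9.5/95 = 10% to (9.5 + 20(1 − h)) / (95 − 20h).

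| h | Gated share after | Gated change |
|---|---|---|
| 50% | 19.5/85 = 22.9% | 12.9 points |
| 75% | 14.5/80 = 18.1% | 8.1 points |
| 100% | 9.5/75 = 12.7% | 2.7 points |

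At h = 100% the gate contains no new producer. The 2.7 points come only from the smaller denominator. At h = 0 the gated share is 29.5/95 = 31.1% and nothing is lost, so the attenuation depends on how many new producers leave the gate.

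**Other markers.** The same denominator effect can run against an expectation. Suppose 90 of 100 cells are CD28+, 9 of those are IL-4+, and 20 IL-4-negative cells leave the gate. The gated IL-4 share goes from 9/90 = 10% to 9/70 = 12.9% with no added IL-4 production, whereas 13.2.2 expects a decrease. If IL-4+ cells left preferentially, the gated share would fall instead. The documents do not say which cells leave, so no direction can be assigned.

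**The case against.** **Graded fall and no threshold.** Section 1.2 describes less CD28, not its loss, and 13.4.2 treats CD28 as continuous. A reader might infer that the gate removes the CD28-low cells as a class. The documents do not support that: with no cut-off stated, dim cells may stay inside. This stands. Only CD28-negative cells are certain to be excluded.

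**SU.** The section 9 anergy row might suggest that the gate empties most completely in SU participants, leaving a handful of cells or an undefined measure. That row belongs to a general CyTOF table and is not stated for CD154+ cells; the separate row for allergen specific cells does not mention CD28. Under the plan's 20% shift, a 90% CD28+ share would fall to 70%, leaving 70 of 100 cells. This also stands.

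**Assumed shares.** It is tempting to say that the effect disappears. That holds only in Case 1, by construction; Case 2 gives attenuation in the same direction. Nor do the documents tie IL-10, TGF-beta, GPR15, CCR4 or CRTh2 to CD28 status, so a general bias toward no change is not shown.

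**Ungated work elsewhere.** Section 13.7 plans bulk sorting of activation-positive cells for all participants, which largely answers the TCR part in practice. Section 9 lists ungated comparisons that could occur, and section 3.4 compares tetramer+ phenotypes. The primary and first secondary endpoints would show CD28 itself falling. None of this changes the endpoint definition, which is gated in all three places. The section 9 comparisons are only possible ones, the tetramer work is exploratory, and tetramer sorting of single cells is expected in at least 60% of participants.

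**Status.** Section 13.4.4 calls secondary findings hypothesis generating. That lowers the severity. It speaks to false positives, though, not to an endpoint that may miss the predicted change. Function within CD28+ cells could be a legitimate question, but the plan gives no rationale for choosing it.

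**Conclusion.** The concern holds in a limited form. As written, the eight measures are conditioned, after treatment, on the variable that forms the primary outcome, and their cell population does not match that of the primary endpoint or of the plan's own Expectations. CD28-negative cells are excluded and CD28-dim cells may be. A true IFN-gamma rise in responders may be attenuated, or missed if it lies wholly in CD28-negative cells.

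Under the plan's 20% shift and the assumed shares, the ungated rise is 3 to 20 points, against a gated change of none to about 13 points. The upper gated figure assumes that at least half of the new producers lose CD28. These are illustrations, not estimates for this trial. For the other markers the distortion has no known direction.

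The primary endpoint, its test and its power are untouched. This is a should-fix for hypothesis-generating secondary endpoints.

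**What to change.** In the synopsis, 3.3 and 13.2.2, define the cytokine and receptor measures in all CD4+ allergen-specific (CD154+) T cells, the population of the primary endpoint. Name that population in 13.4.4 as well. State the CD28 positivity threshold, and report the CD28+ and CD28- subsets as a supportive breakdown, which keeps the gated results available. For CDR3b diversity, align the endpoint wording with the activation-positive bulk sort in 13.7.

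The cost is endpoint rewording and re-gating of the same cytometry data, with no extra samples. This assumes that CD28-negative CD154+ events are recorded and not discarded at acquisition, which the sponsor should confirm. The primary analysis does not change.
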